9.4. Statistical Analyses

Statistical analysis of this study will be the responsibility of sponsor or its designee.

Any change to the data analysis methods described in the protocol will require an amendment only if it changes a principal feature of the protocol. Any other change to the data analysis methods described in the protocol, and the justification for making the change, will be described in the statistical analysis plan (SAP). Additional exploratory analyses of the data will be conducted as deemed appropriate.

The SAP will be finalized prior to the first participant dosed and it will include a more technical and detailed description of the statistical analyses described in this section. This section is a summary of the planned statistical analyses of the most important endpoints including primary and key secondary endpoints.

9.4.1. General Considerations

Method	Analysis
Descriptive Statistics	number of participants, mean, standard deviation,
	median, minimum, and maximum for continuous
	measures, and frequency counts and percentages for
	categorical measures
Kaplan-Meier curves and summary statistics	Time-to-event analysis
Logistic regression analysis	Treatment comparisons of binary variables with
	treatment in the model.
Nonparametric	Treatment comparison of ordinal variables.
(for example, Mann-Whitney or van Elteren tests)	
Analysis of variance or analysis of covariance	Treatment comparisons of continuous variables
	following appropriate transformations, if necessary

This table describes the general statistical methods that may be used in this study.

Adjustments for other factors, if any, will be described in the SAP.

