9.4.4. Exploratory Endpoints

Exploratory endpoints will be summarized using descriptive methodology and treatment comparisons conducted using methods previously described.

Endpoints will include:

- Duration (days) of hospitalization
- Proportion (percentage) of participants admitted to ICU
- Proportion (percentage) of participants requiring mechanical ventilation
- Score on the NIAID ordinal scale at pre-specified time points
- Score on the WHO ordinal scale at pre-specified time points
- Proportion (percentage) of participants with at least a 2-point improvement on the WHO ordinal scale or live discharge from hospital, at pre-specified time points
- Proportion (percentage) of participants with at least a 2-point improvement on the NIAID ordinal scale or live discharge from hospital at pre-specified time points
- NEWS2 score at pre-specified time points
- Proportion (percentage) of participants with any worsening on the NIAID ordinal scale from baseline to Day 15, and
- Comparison from baseline to Day 29 for the emergence of viral resistance to LY3819253.

Mortality and categorical changes on the ordinal scale will be analyzed as discrete variables.

Additional exploratory analyses of the data will be conducted as deemed appropriate. Study results may be pooled with the results of other studies for safety, pharmacodynamic, or

population PK analysis purposes to avoid issues with post-hoc analyses and incomplete disclosures of analyses.

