10. STATISTICAL METHODOLOGY

10.1 General

Data listings will be provided for all data that is databased. Summary statistics and statistical analysis will only be presented for data where detailed in this SAP. For continuous data, summary statistics will include the arithmetic mean, arithmetic standard deviation (SD), median, min, max and N; for log-normal data (e.g. the PK parameters: AUCs and maximum observed drug concentration $[C_{max}]$) the geometric mean and geometric coefficient of variation (CV%) will also be presented. For categorical and ordinal data, frequency count and percentages will be presented. Data listings will be provided for all participants up to the point of withdrawal, with any participants excluded from the relevant population highlighted. Summary statistics and statistical analyses will generally only be performed for participants included in the relevant analysis population. For the calculation of summary statistics and statistical analysis, unrounded data will be used.

Mean change from baseline is the mean of all individual participants' change from baseline values. Each individual change from baseline will be calculated by subtracting the individual participant's baseline value from the value at the timepoint. The individual participant's change from baseline values will be used to calculate the mean change from baseline using a SAS procedure such as Proc Univariate.

Data analysis will be performed using SAS[®] Version 9.4 or greater.

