10.5 Efficacy Assessments

10.5.1 Hospitalization and clinical events, clinical status, and environmental risk factors

All hospitalization events, procedures of special interest, and environmental risk factors will be listed.

The following data will be summarized by treatment using descriptive statistics:

• Duration of hospitalization (in days);

- Score on the NIAID ordinal scale at pre-specified time points;
- Score on the WHO ordinal scale at pre-specified time points;
- NEWS2 score at pre-specified time points.

The following data will be summarized by treatment using frequency tables:

- Proportion (percentage) of participants admitted to ICU;
- Proportion (percentage) of participants requiring mechanical ventilation;
- Proportion (percentage) of participants with at least a 2 point improvement on the NIAID scale or live discharge from hospital from baseline at any time during the study;
- Proportion (percentage) of participants with at least a 2-point improvement on the WHO ordinal scale or live discharge from hospital from baseline at any time during the study;
- Proportion (percentage) of participants with any worsening on the NIAID ordinal scale from baseline to Day 15;
- Proportion (percentage) of participants with at least a 2-point worsening on the NIAID ordinal scale from baseline at any time during the study;
- Consciousness level score assessed by NEWS2;
- Severity of pre specified clinical events (fever, cough, and shortness of breath).

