12. CHANGES FROM THE PROTOCOL SPECIFIED STATISTICAL ANALYSES

There were no changes from the protocol specified statistical analyses.

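### The SAP plans no between-arm comparison of any clinical endpoint and no handling of deaths, contrary to protocol 9.4.4, yet declares no change from the protocol

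*Protocol*

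**What the plan says.** **Protocol.** The table in 9.4.1 pairs ordinal variables with nonparametric treatment comparison ("for example, Mann-Whitney or van Elteren tests") and binary variables with logistic regression. The table is permissive: "This table describes the general statistical methods that may be used in this study". Section 9.4.4 is firmer: "Exploratory endpoints will be summarized using descriptive methodology and treatment comparisons conducted using methods previously described". Its list contains the NIAID, WHO and NEWS2 scores, the improvement and worsening proportions, ICU admission and mechanical ventilation. It adds: "Mortality and categorical changes on the ordinal scale will be analyzed as discrete variables". Section 9.4 requires changes of method that do not need an amendment to be described and justified in the SAP.

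**SAP.** Section 10.5.1 opens its first list with "The following data will be summarized by treatment using descriptive statistics"; that list includes "Score on the NIAID ordinal scale at pre-specified time points" and the WHO and NEWS2 scores. Its second list gives the proportions, including NIAID worsening by Day 15, as frequency tables. Neither list carries a test, model or interval. Section 10.1 limits output: "Summary statistics and statistical analysis will only be presented for data where detailed in this SAP". Section 3 gives the SAP precedence over the protocol's statistical section and undertakes to identify substantial differences. Section 12 states: "There were no changes from the protocol specified statistical analyses".

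**The concern.** Clinical status is a main place where benefit or harm would show in this study. Protocol 10.3.1 exempts COVID-19 hypoxemia and respiratory failure from adverse event reporting unless the investigator considers them related, and under 10.3.2 an event that is not an AE cannot be an SAE. Protocol 4.2 gives the detection of less clinical worsening as the reason for Cohort 4. An SAP with no comparison of that outcome leaves the stated purpose of up to 100 participants without a specified analysis.

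The sponsor is unblinded throughout, so a comparison chosen later would be chosen with the data in view. A score summary with no rule for deaths can also understate a difference if participants who die drop out of the later time points.

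**Working it through.** **1. Promise against plan.**

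| Endpoint | Protocol 9.4.4 with 9.4.1 | SAP 10.5.1 |
|---|---|---|
| NIAID and WHO scores | Descriptive summary and nonparametric comparison | Descriptive statistics |
| NIAID worsening by Day 15, ICU, ventilation | Descriptive summary and logistic comparison | Frequency tables |
| Mortality | Analysed as a discrete variable | Not mentioned |

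The SAP's inferential or model-based analyses cover only PK dose proportionality, viral load, viral load AUC and viral clearance.

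**2. Is it a version lag?** SAP 3 says the SAP was written after Amendment (a). The amendment history shows that (a) had already updated 9.4.1 and 9.4.4, and the current amendment's change table lists neither section. Timing does not explain the gap.

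**3. The plan's own power figure.** Planned numbers: placebo 3 x 2 + 50 = 56; LY3819253 3 x 6 + 50 = 68. With 22% v 9% and one-sided alpha 0.05:

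- Pooled rate = (56 x 0.22 + 68 x 0.09)/124 = 0.1487
- Null SE = sqrt(0.1487 x 0.8513 x (1/56 + 1/68)) = 0.0642
- Alternative SE = sqrt(0.22 x 0.78/56 + 0.09 x 0.91/68) = 0.0653
- z = (0.13 - 1.645 x 0.0642)/0.0653 = 0.373, so power is 64.6%

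A Wald log-odds approximation gives 62.7% and Fisher's exact test 57.2%. With the 9 permitted additional participants (133 in total) Fisher gives 58.3-59.3%. The stated 60% lies within this range and is not in dispute. The point is that the SAP contains no comparison to which it applies.

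**4. What a rank test could add (illustration only).** The documents give no score distribution. Two 8-category distributions were assumed for placebo, worst (death) to best:

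- A: 6, 8, 5, 8, 8, 5, 20, 40%
- B: 4, 5, 3, 5, 3, 2, 8, 70%

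The shift is proportional odds. The odds ratio implied by 22% v 9% is (0.22/0.78)/(0.09/0.91) = 2.85; carrying it from worsening over to the score is itself an assumption. Simulated one-sided, unstratified Mann-Whitney power at 56 v 68:

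| Odds ratio | A | B |
|---|---|---|
| 1.5 | 33-34% | 24% |
| 2.0 | 67-68% | 50% |
| 2.85 | 92% | 75% |

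If the effect is confined to the worst four of eight categories, power is about 39%, below the binary comparison. That figure depends on where the spared participants land and falls if they improve by only one category. At 6 v 6, as in one dose cohort against the pooled placebo of Cohorts 1-3, power under A is about 9%, 13% and 21% at the three odds ratios.

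**5. Deaths.** Under A, excluding deaths instead of ranking them worst lowers power to about 30%, 59% and 88%.

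**6. Pooling.** Allocation is 3:1 in Cohorts 1-3 and about 1:1 in Cohort 4. Cohorts 1-3 would supply 18/68 = 26% of the LY3819253 arm but 6/56 = 11% of placebo. An unstratified pooled test would mix cohort differences into the treatment effect.

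**The case against.** The tests are exploratory and unadjusted (protocol 9.1) in a Phase 1 safety study, and the 9.4.1 table only says what may be used. SAP 3 allows additional analyses if the CSR identifies them. This stands so far as it goes: no particular rank test is mandatory, and a comparison could still be run. It does not remove the commitment in 9.4.4 that comparisons will be made, or the incorrect statement in SAP 12.

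A reader might infer more than the documents support:

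- **That the most informative clinical comparison was dropped.** The documents size the binary worsening endpoint, and the rank test can do worse than it.
- **That SAP 10.5.1 contradicts SAP 10.1 by not tabulating categories.** SAP 10.1 already prescribes frequencies and percentages for ordinal data, so no separate change is needed.
- **That a rank test was promised for NEWS2.** The protocol does not class NEWS2 as ordinal.
- **That the scores will be summarised over survivors only.** No such rule is written. The scales are not reproduced, and death may already be a category. The clinical-status items in protocol 8.2.6 have no death entry and the SAP is silent, so the handling is unspecified.
- **That deaths will be invisible.** They may appear in the disposition summary or the SAE listing, although a COVID-19 death may fall under the AE exemptions. Neither output is the mortality analysis that the protocol promises.

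**Conclusion.** The mismatch is established from the text alone: protocol 9.4.4 commits to comparisons and a mortality analysis, SAP 10.5.1 plans neither for any clinical endpoint, and SAP 12 declares no change. The missing death rule holds for the SAP text available here, which does not include section 14.3 on insufficient data.

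The gap covers the Day 15 worsening endpoint as well as the ordinal scores. The primary safety objective is unaffected. Any gain from a rank test (75-92% against about 65%) is conditional on the assumed distributions, roughly proportional odds and enrolment of optional Cohort 4. It is a reason to add the test beside the worsening endpoint, and no basis for replacing it. The point should be settled in the SAP before further unblinded data are reviewed.

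**What to change.** In SAP 10.5.1 add:

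- **(a) Ordinal scores.** A van Elteren comparison of the NIAID and WHO scores, LY3819253 v placebo, at named study days taken from the Schedule of Activities. Stratify by cohort whenever cohorts are pooled. Report the Mann-Whitney probability with a 90% CI, matching the intervals used elsewhere in the SAP.
- **(b) Worsening.** The logistic comparison, or an exact one, for any NIAID worsening by Day 15.
- **(c) Deaths.** A participant who dies takes the worst category at every later time point, and counts as worsened if death is by Day 15. Add a mortality summary by arm.

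A rank test for NEWS2 is optional. If the comparisons are not wanted, correct SAP 12 to say that they were dropped and why.

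Cost: SAP wording and a few tables, with no extra participants or visits. Confirm that the date of death is captured for COVID-19 deaths that fall outside AE reporting.

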9.4.2. Safety Analyses

Safety analyses will be conducted using the safety population described above.

All investigational product and protocol procedure AEs will be listed, and if the frequency of events allows, safety data will be summarized using descriptive methodology.

The incidence of AEs for each treatment will be presented by severity and by association with intervention as perceived by the investigator. Adverse events reported prior to randomization will be distinguished from those reported as new or increased in severity during the study post-randomization.

Safety parameters that will be assessed include, but are not limited to, safety laboratory parameters, and vital signs. The parameters will be summarized using standard descriptive statistics. Additional analysis will be performed if warranted upon review of the data.

9.4.3. Pharmacokinetic and Pharmacodynamic Analyses

Pharmacokinetic analyses will be conducted on data from all participants who receive intervention and have evaluable PK.

Pharmacokinetic parameter estimates for LY3819253 will be calculated using standard noncompartmental methods of analysis.

The primary parameter for analysis will be mean concentration on Day 29. Other noncompartmental parameters, such as half-life, apparent clearance, and apparent volume of distribution, may be reported.

Pharmacodynamic endpoints will be summarized using descriptive methodology.

The SARS-CoV-2 viral dynamics will include evaluation of

- Change from baseline in SARS-CoV-2 viral load (Days 7, 11, 15 and 22)
- Viral load AUC
- Time to SARS-CoV-2 clearance, and
- Proportion of participants that achieve SARS-CoV-2 clearance.

Additional PK/PD concentration-response analysis may be performed.

9.4.4. Exploratory Endpoints

Exploratory endpoints will be summarized using descriptive methodology and treatment comparisons conducted using methods previously described.

Endpoints will include:

- Duration (days) of hospitalization
- Proportion (percentage) of participants admitted to ICU
- Proportion (percentage) of participants requiring mechanical ventilation
- Score on the NIAID ordinal scale at pre-specified time points
- Score on the WHO ordinal scale at pre-specified time points
- Proportion (percentage) of participants with at least a 2-point improvement on the WHO ordinal scale or live discharge from hospital, at pre-specified time points
- Proportion (percentage) of participants with at least a 2-point improvement on the NIAID ordinal scale or live discharge from hospital at pre-specified time points
- NEWS2 score at pre-specified time points
- Proportion (percentage) of participants with any worsening on the NIAID ordinal scale from baseline to Day 15, and
- Comparison from baseline to Day 29 for the emergence of viral resistance to LY3819253.

Mortality and categorical changes on the ordinal scale will be analyzed as discrete variables.

Additional exploratory analyses of the data will be conducted as deemed appropriate. Study results may be pooled with the results of other studies for safety, pharmacodynamic, or

population PK analysis purposes to avoid issues with post-hoc analyses and incomplete disclosures of analyses.

9.4.5. Immunogenicity

If data from validated immunogenicity assays are available, treatment-emergent anti-drug antibodies (TE-ADAs) may be assessed.

Treatment-emergent ADAs are defined as participants

- with a 2-fold (1 dilution) increase in titer than the minimum required dilution if no ADAs were detected at baseline (treatment-induced ADA) or
- with a 4-fold (2 dilutions) increase in titer compared with baseline if ADAs were detected at baseline (treatment-boosted ADA).

The frequency and percentage of participants with preexisting ADA and who are TE-ADA positive (TE-ADA+) to LY3819253 will be tabulated.

The distribution of titers and frequency of neutralizing antibodies (if assessed) for the TE-ADA+ participants may also be tabulated.

The relationship between the presence of antibodies and PK parameters, PD response or safety to LY3819253 may also be assessed. Additional details may be provided in the SAP.

9.5. Interim Analyses

Periodic, unblinded reviews of PK, PD and safety data will occur throughout the study in addition to the scheduled dose escalation reviews.

If Cohort 4 proceeds, then up to 4 interim analyses may occur.

Monitoring of unblinded safety data (including AEs, SAEs, and selected laboratory measurements) will occur throughout the study and will be conducted by the ISAC. Details of the unblinded safety reviews, including the frequency and approximate timing, are specified in the ISAC charter.

The approximate timing, decision criteria, and statistical methods associated with each possible modification to the ongoing study will be fully described in the SAP and ISAC Charter and finalized prior to the first study unblinding.

9.6. Data Monitoring Committee (DMC)

This study will not have a data monitoring committee. Independent safety assessment committee information is in Section 10.1.5 and the ISAC charter.

10. Supporting Documentation and Operational Considerations

10.1. Appendix 1: Regulatory, Ethical, and Study Oversight Considerations

10.1.1. Regulatory and Ethical Considerations

This study will be conducted in accordance with the protocol and with the following:

- Consensus ethical principles derived from international guidelines including the Declaration of Helsinki and Council for International Organizations of Medical Sciences (CIOMS) International Ethical Guidelines
- Applicable International Council for Harmonization (ICH) Good Clinical Practice (GCP) Guidelines, and
- Applicable laws and regulations.

The protocol, protocol amendments, ICF, IB, and other relevant documents (e.g., advertisements) must be submitted to an IRB/IEC by the investigator and reviewed and approved by the IRB/IEC before the study is initiated.

Any amendments to the protocol will require IRB/IEC approval before implementation of changes made to the study design, except for changes necessary to eliminate an immediate hazard to study participants.

The investigator will be responsible for the following:

- Providing written summaries of the status of the study to the IRB/IEC annually or more frequently in accordance with the requirements, policies, and procedures established by the IRB/IEC
- Notifying the IRB/IEC of SAEs or other significant safety findings as required by IRB/IEC procedures, and
- Providing oversight of the conduct of the study at the site and adherence to requirements of 21 CFR, ICH guidelines, the IRB/IEC, and all other applicable local regulations.

Investigator sites are compensated for participation in the study as detailed in the clinical trial agreement.

10.1.2. Financial Disclosure

Investigators and sub-investigators will provide the sponsor with sufficient, accurate financial information as requested to allow the sponsor to submit complete and accurate financial certification or disclosure statements to the appropriate regulatory authorities. Investigators are responsible for providing information on financial interests during the study and for 1 year after completion of the study.

10.1.3. Informed Consent Process

The investigator or their representative will explain the nature of the study, including the risks and benefits, to the participant or their legally authorized representative and answer all questions regarding the study.

Participants must be informed that their participation is voluntary. Participants or their legally authorized representative will be required to sign a statement of informed consent that meets the requirements of 21 CFR 50, local regulations, ICH guidelines, Health Insurance Portability and Accountability Act (HIPAA) requirements, where applicable, and the IRB/IEC or study center.

Due to strict respiratory isolation policies, limited access to COVID-19 patient rooms and SARS-CoV-2 transmissibility via droplet-contaminated paper, verbal consent and alternative methods of obtaining consent (for example, by phone) will be allowed if approved by the IRB.

If a signed paper copy of the ICF is allowed by hospital policy, how it will be obtained and stored will need to be determined. Any variation from the standard consent process due to isolation and infection control should be sent to the IRB for approval prior to enrollment.

The site should document the process in their regulatory files and demonstrate that the process has IRB concurrence or approval.

The medical record must include a statement that written informed consent was obtained before the participant was entered in the study and the date the written consent was obtained. The authorized person obtaining the informed consent and, if applicable, the individual designated to witness a verbal consent, must also sign the ICF.

Participants must be re-consented to the most current version of the ICF(s) during their participation in the study.

A copy of the ICF(s) must be provided to the participant or the participant's legally authorized representative and is kept on file.

10.1.4. Data Protection

Participants will be assigned a unique identifier by the sponsor. Any participant records, datasets or tissue samples that are transferred to the sponsor will contain the identifier only; participant names or any information which would make the participant identifiable will not be transferred.

The participant must be informed that their personal study-related data will be used by the sponsor in accordance with local data protection law. The level of disclosure must also be explained to the participant who will be required to give consent for their data to be used as described in the informed consent.

The participant must be informed that their medical records may be examined by Clinical Quality Assurance auditors or other authorized personnel appointed by the sponsor, by appropriate IRB/IEC members, and by inspectors from regulatory authorities.

The sponsor has processes in place to ensure data protection, information security and data integrity. These processes include appropriate contingency plan(s) for appropriate and timely response in the event of a data security breach.

